7.1 Demographic and Baseline Characteristics

Demographics and Baseline characteristics will be summarized for RZB, RZB_NL, Retreatment, UST_RZB, ADA_RZB, FUM_RZB, RZB_Japan populations. Continuous variables will be summarized with the number of non-missing observations by mean, standard deviation, first quartile, median, third quartile, minimum and maximum values. Categorical data will be summarized using frequencies and percentages. No Statistical tests will be performed for this study.

The following demographic and baseline parameters will be summarized.

Subject Demographics

- Sex (male, female)
- Age (years), defined as the number of years from date of birth to date of first drug
- Age categories (< 40 years, ≥ 40 – < 65 years, ≥ 65 years.)
- Race (American Indian or Alaska Native, Asian, Black or African American, Native Hawaiian or Other Pacific Islander, White, Multi Race)
- Ethnicity (Hispanic or Latino, Not Hispanic or Latino)

- Body weight (kg)
- Body weight category (≤ 100 kg, > 100 kg)
- Height (cm)
- BMI (kg/m^2)
- BMI category (< 25 , $\geq 25 - < 30$, ≥ 30)
- Prior exposure to TNF antagonists (0 versus ≥ 1)

General Baseline Characteristics

- PASI (Psoriasis Area and Severity Index)
- BSA (Body Surface Area)
- sPGA (Static Physician Global Assessment)
- NAPSI (Nail Psoriasis Severity Index)
- PSSI (Psoriasis Scalp Severity Index)
- PPASI (Palmoplantar Psoriasis Area Severity Index)
- Dermatology Life Quality Index (DLQI)

Psoriasis and Cardiovascular History

- Psoriatic arthritis (diagnosed, suspected, no)
- Cardiovascular Diseases (myocardial infarction, angina pectoris, transient ischemic attack, stroke, deep vein thrombosis)
- Cardiovascular Risk Factors (hypertension, hyperlipidemia, diabetes mellitus, obesity)

General Use

- Smoking status (Never-smoked, Ex-smoker, Currently smokes)
- Alcohol status (Non-drinker, drinks – no interference, drinks – possible interference)

Prior Treatment:

- Psoriasis Biologic Treatment History – by Response to Prior Treatment
- Psoriasis Treatment – by Therapy Type (topical therapy, phototherapy, photochemotherapy, non-biologic systemic therapy, TNF antagonist, other biologic)

Also, Physical Exam and Pregnancy Test will be presented in listing format.

7.2 Medical History

Medical history (at the time of enrollment in the preceding study as well as new information and updates collected in this study) will be summarized using body systems and condition/diagnosis as captured on the eCRF for the All Risankizumab Treated Population. The body systems will be presented in alphabetical order and the conditions/diagnoses will be presented in alphabetical order within each body system. The number and percentage of subjects with a particular condition/diagnosis will be summarized for each treatment arm. Subjects reporting more than one condition/diagnosis within a body system will be counted only once for that body system.

7.3 Previous Treatment and Concomitant Medications

Prior and concomitant medications will be summarized for the ALL_RZB Population by generic name. A prior medication is defined as any medication taken at the time of entry into the study and prior to the first dose of risankizumab. A concomitant medication is defined as any medication that started prior to the first dose of risankizumab and continued to be taken after the first dose of risankizumab or any medication that started after the first dose of risankizumab, but not after the last dose of risankizumab + 140 days. The number and percentage of subjects who had taken medications will be summarized by generic drug name assigned by the World Health Organization (WHO) for both prior and concomitant medications.

7.4 Protocol Deviation

Number and percentage of subjects who reported at least one of the following protocol deviation categories will be provided in the ALL_RZB Population.

- Subject entered into the study even though she/he did not satisfy entry criteria
- Subject who developed withdrawal criteria during the study and was not withdrawn
- Subject who received wrong treatment or incorrect dose
- Subject who received excluded or prohibited concomitant medication?

8.0 Patient Disposition

For each population, the number of subjects for each of the following categories will be summarized.

- Number of subjects treated in Study M15-997
- Subjects completed or ongoing Study M15-997
- Subjects who discontinued study drug in Study M15-997
- Subjects who discontinued the Study M15-997

A table show the number and percent of subjects by the preceding study and treatment group in the preceding study will be presented.

In addition, the number and percentage of subject who discontinued the study drug will be summarized by reason (primary and all).

9.0 Study Drug Exposure and Compliance

Study drug exposure (days) will be summarized using the sample size, mean, standard deviation, minimum, median and maximum. Study drug exposure will be summarized as follows:

Risankizumab Exposure (in Days):

The Risankizumab Exposure (total duration during the preceding study and Study M15-997) will be defined as follows:

The Risankizumab Exposure = Last risankizumab dose date – First risankizumab dose date (either in Study M15-997 or preceding study) + 84 days, except:

- The Risankizumab Exposure in the Retreatment Population is defined as: Last risankizumab dose date – First retreatment of risankizumab date (either in Study M15-997 or preceding study) + 84 days
- The Risankizumab Exposure in the ALL_RZB Population among subjects who were re-randomized to placebo during Study 1311.4 Part B is defined as: Last risankizumab dose date during Study 1311.4 Part A – First risankizumab dose date + 84 days + Last risankizumab dose date – First retreatment of risankizumab date + 84 days

In addition, number of subjects who have at least one dose of self-injected study drug during Study M15-997 will also be summarized.

A data cutoff date (September 01, 2017) was applied during the first interim analysis in 2017.

A data cutoff date (November 01, 2021) will be applied during the second interim analysis. The duration of study drug exposure will be defined up to this cutoff date.

10.0 Efficacy Analysis

10.1 General Considerations

The efficacy analysis will be performed for each population except the ALL_RZB Population. The efficacy analysis will use the data from this study and preceding study after subjects started to take risankizumab. The BL values (baseline values from the

preceding studies) will be used to determine responses and changes in the efficacy variables.

Continuous variables will be summarized by the number of observations, mean, standard deviation, median, minimum, maximum, 25th and 75th percentiles, as well as the 95% confidence intervals (CIs) of the mean values. Categorical variables will be summarized by counts and percentages, as well as the 95% CIs of the percentages. No statistical tests will be performed in this study.

Missing data will be imputed using the following methods for the efficacy analyses:

- Last Observation Carried Forward (LOCF): The LOCF analyses will use the last observed non-missing evaluation (last completed non-missing evaluation, from composite endpoint) from the previous visit within the particular period for efficacy measures assessed to impute missing data at later visits in the same period. Baseline efficacy evaluations will not be carried forward. Of note, post-baseline observations from Part A1 in Study 1311.4 can be carried forward to ITT_A2 subjects from ARM 1 since treatment is the same.
- As-Observed Cases (OC): The as-observed analysis will not impute values for missing evaluations, and thus a subject who does not have an evaluation on a scheduled visit will be excluded from the as-observed analysis for that visit.

LOCF will be used as the primary imputation method and OC will be used as sensitivity analysis for both categorical variables and continuous variables. Both LOCF and OC will not include values after discontinuation of study drug.

All endpoints will be analyzed up to the last visit with at least one subject has observed measurements of that variable, by the time of the interim data cutoff.

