All subjects will be administered 150 mg risankizumab s.c. at the Baseline visit.

Treatment Period

From the Baseline visit onwards, risankizumab will be administered subcutaneously E12W during the study.

Figure 1. Study Schematic

Study visits for dosing, efficacy and safety assessments will be performed E12W starting from Baseline until the Week 156 visit. After this visit until the End of Treatment (EOT) visit at Week 252, study visits will be performed E24W. There is a ± 7 days visit window for study visits. Every effort will be made to bring subjects back to their original scheduled visit (calculated from Baseline) if they are out of the visit window.

At Weeks 168, 192, 216 and 240, subjects will self-administer risankizumab at home after proper training to the subject and/or caregiver on the injection technique with the pre-filled syringe at Week 156 by the site staff. Alternatively, subjects may receive the injection of study drug of Weeks 168, 192, 216 and 240 at the study site. Subjects who discontinue study drug treatment early will need to attend an early EOT visit ideally within 2 weeks after the decision and preferably prior to the administration of any new therapies (Section 5.4.1).

End of Observation Visit

All subjects, including those that prematurely discontinued study drug treatment, will have an End of Observation Visit (EOO) via phone, approximately 20 weeks after their last administered dose of study drug. Study completion is defined as a subject having completed the EOO visit.

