- If the subject experiences an intolerable increase of psoriasis during the course of the study the subject will be discontinued from the study drug to receive rescue treatment as deemed appropriate by the investigator.
- If the subject experiences a serious infection, the study drug should be held until the infection is resolved or stabilized. The study drug dosing visit could

be postponed such that the study drug of the following visit will not be administered within 14 days. If the subject has not received study drug due to this serious infection for at least 24 weeks, the subject will be permanently withdrawn from study drug.

If, during the course of study drug administration, the subject prematurely discontinues study drug use, the subject has the option to continue in the study and complete the remaining visits as scheduled. If remaining visits will be completed, an early EOT visit is not required. If the subject does not continue in the study, the procedures outlined for the early EOT visit must be completed, ideally within 2 weeks of the decision and preferably prior to the initiation of another therapy. However, these procedures should not interfere with the initiation of any new treatments or therapeutic modalities that the Investigator feels are necessary to treat the subject's condition. For subjects that prematurely discontinue, study drug will not be given at the early EOT visit and subjects should have the telephonic EOO visit, 20 weeks after their last administered dose of study drug to determine the status of any ongoing AEs/SAEs or the occurrence of any new AEs/SAEs.

Following discontinuation of the study drug, the subject will be treated in accordance with the Investigator's best clinical judgment.

All attempts must be made to determine the primary reason for premature discontinuation. The information will be recorded on the appropriate eCRF page.

For subjects that are considered lost to follow-up, reasonable attempts must be made to obtain information on the final status of the subject. At a minimum, two phone calls must be made and one certified letter must be sent and documented in the subject's source documentation.

Interruption/Discontinuation of Study Drug Due to COVID-19

For subjects with documented COVID-19, the timing of next administration of study drug or possibility of premature discontinuation from study drug should be discussed with the AbbVie Medical Contact.

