b. Premature discontinuation: For subjects who prematurely discontinue the study before study end (for any reason) an early EOT visit is required.

If the decision to discontinue study participation is made at a regular study visit, the visit should be turned into an EOT visit, i.e., an EOT visit is to be performed instead of the scheduled visit.

If the decision to discontinue study participation is made in between study visits, an EOT visit is to be scheduled at the earliest convenience or at the latest the next upcoming visit according to the Flow Chart. This early EOT visit will include the same procedures as the normal EOT visit and the subject will subsequently enter a follow up period of 20 weeks, until a final EOO visit is performed.

- c. Informed consent must not be signed before the date of the last visit in the preceding study, but needs to be completed prior to initiation of any Study M15-997 study procedures.
- d. The subject's demographic data has been collected at the screening visit of the preceding study, so does not need to be collected again.
- e. Medical history collected in the preceding study will be used in Study M15-997. Only new information and updates will need to be collected at the Study M15-997 Baseline visit.
- f. For subjects rolling over from the preceding study with ≤ 4 day delay from the last visit per protocol in the preceding study, these procedures do not need to be repeated if already performed at this last visit of the preceding study. Results assessed at this last visit will serve as Baseline visit results for Study M15-997. Subjects initiating the OLE with a delay of > 4 days from completion of the last visit per protocol in the preceding study will need to complete all activities for Baseline.
- g. New Adverse Events or unresolved Adverse Events from the preceding study to be followed up in this study.
- h. Symptom directed physical exam.
- i. Vital Signs must precede blood sampling and must be assessed pre-dose at all dosing visits. Additional vital signs assessments should be made 5 (± 2) minutes post-dose and 60 (± 10) minutes post-dose at Visit 1 and Visit 2.
- j. Only subjects that had a negative TB test during the last testing in the preceding study or Study M15-997 will be tested for TB.
- k. Urine pregnancy testing at every dosing visit. Additional serum pregnancy testing will occur in case of a positive urine test result at any visit.

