6.0 Analysis Conventions

Since this is an open-label continuation study, no statistical test will be conducted. Summary statistics will be provided. Data from preceding studies will be integrated with data from this study in the summaries.

Definition of Baseline

For this study, the following two types of baseline values are defined.

1. Preceding Study Baseline Value (BL): These values represent the baseline values of preceding studies, that is, the last non-missing values on or before the date of the first dose of study drug in the preceding study. For vital sign assessments, only assessments prior to first dose time will be considered, since vital signs are to be assessed both pre- and post-dose in some visits. The efficacy analysis based on RZB, RZB_NL, Retreatment, UST_RZB, ADA_RZB, FUM_RZB, and RZB_Japan populations will use these baseline values. These baseline values will be referred to as "BL" in this document. Unless otherwise specified, this will be the "baseline" for analysis.
2. RZB baseline value (BL_RZB): These values are the last non-missing values on or before the date of the first dose of risankizumab in the preceding study or Study M15-997. For vital sign assessments, only assessments prior to first dose time will be considered, since vital signs are to be assessed both pre- and post-dose in some visits. These values will be referred to as BL_RZB in this document. BL_RZB will be used for safety analyses in all populations.

Definition of Final Observation (Applicable to Safety Analyses)

Final observation in the entire study is defined as the last non-missing observation collected within 140 days after the last dose of risankizumab.

Definition of Rx Days (Days Relative to the Date of First Dose of Study Drug)

Rx days are calculated for each time point relative to the date of first dose of risankizumab in the corresponding study period. They are defined as the number of days between the day of the first dose of risankizumab and the specific time point. Rx days are negative values when the time point of interest is prior to the first risankizumab dose day. Rx days are positive values when the time point of interest is on or after the first risankizumab dose day. The day of the first dose of risankizumab is defined as Rx Day 1, while the day prior to the first risankizumab dose is defined as Rx Day -1 (there is no Rx Day 0).

Definition of Analysis Windows

All time points and corresponding time windows are defined based on Rx Days.

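### SAP 10.1 drops values after an undated drug stop from both LOCF and OC, and no efficacy analysis counts stopping for worsening psoriasis as non-response

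*SAP*

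**What the plan says.** SAP 10.1 plans two methods for missing efficacy data: LOCF as primary and OC as sensitivity, for categorical and continuous variables alike. It then states: "Both LOCF and OC will not include values after discontinuation of study drug". No date is attached to that event. Protocol 8.1.4 names the same two methods without the exclusion, and leaves data-handling conventions to the SAP.

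Protocol 5.4.1 makes worsening disease a reason to stop: "If the subject experiences an intolerable increase of psoriasis during the course of the study the subject will be discontinued from the study drug", with rescue treatment to follow. A subject who stops drug may stay in the study, and then "If remaining visits will be completed, an early EOT visit is not required". For subjects who leave the study, Appendix C, note b, covers two cases. If the decision falls at a regular visit, "the visit should be turned into an EOT visit". If it falls between visits, "an EOT visit is to be scheduled at the earliest convenience or at the latest the next upcoming visit according to the Flow Chart". Protocol 5.4.1 gives no study drug at an early EOT visit. On visit spacing after Week 156, Protocol 5.1 says: "After this visit until the End of Treatment (EOT) visit at Week 252, study visits will be performed E24W".

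Neither SAP 10.1 to 10.5 nor Protocol 8.1.4 contains a rule that scores any discontinuation as non-response. SAP 8.0 counts drug discontinuations by reason, but does not link them to response.

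**The concern.** A subject taken off drug because the psoriasis became intolerable has failed treatment by the protocol's own terms. Neither planned method is built to show that. From the stop onward, OC has no value for the subject, who leaves the denominator. LOCF carries forward whatever value came before the cut, which may be a response recorded before the flare. OC is no check on LOCF here, because it leaves out the same subjects.

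The missing date adds a second problem: two programmers could treat the same early EOT assessment differently, and for worsening stoppers that is the assessment most likely to record the loss of response.

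At stake are the late PASI 90 and sPGA clear or almost clear percentages, which are key variables for the secondary objective of long-term efficacy. There is no hypothesis test, so no error rate or power is involved.

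**Working it through.** **1. Which values survive the exclusion.** The two natural meanings of the cut are the date of the last dose and the date of the decision to stop.

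| Where the flare is recorded | Cut at last dose | Cut at decision date |
|---|---|---|
| Visit at which a dose was still given | kept | kept |
| Visit at which the stop is decided, converted to EOT (no dose given) | dropped | kept (same day) |
| Early EOT after a stop decided between visits | dropped | dropped |
| First scheduled visit after a between-visit stop, subject staying in the study | dropped | dropped |

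LOCF therefore carries the flare in the first row under either date. It can carry a pre-flare value in the last two rows under either date. The second row depends on the undefined date.

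**2. Direction.** Let R = on-drug response rate, d = share off drug by a late visit, w = share of those who stopped for worsening, and q = share of worsening stoppers whose last value used was a response. Other stoppers are assumed to carry a response at rate R.

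- LOCF = (1-d)R + d[(1-w)R + wq]
- LOCF with worsening stops scored as non-response = (1-d)R + d(1-w)R
- LOCF excess = dwq, which is zero only if d, w or q is zero
- OC = R
- OC with worsening stoppers put back as non-responders = (1-d)R / [(1-d) + dw]
- The OC excess is positive whenever dw > 0 and R > 0

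**3. Size, as illustration only.** The plan states no figure to reproduce: neither document gives a discontinuation rate, a split by reason or a response rate for the extension. The only anchor is the Week 16 PASI 90 range of 72-75% in the preceding pivotal studies (Protocol 5.6.4). I take R = 75% from its upper end; d, w and q are assumed.

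With d = 20% and w = 30%:

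- OC with stoppers restored = 0.80 × 0.75 / (0.80 + 0.06) = 0.60 / 0.86 = 69.8%, against 75.0%: excess 5.2 points.
- LOCF with the non-response rule = 0.60 + 0.20 × 0.70 × 0.75 = 70.5%.
- LOCF excess = 0.06 × q: 0 points at q = 0, 3.0 at q = 50%, 4.5 at q = 75%.

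Over d = 10-30% and w = 10-30%:

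| | OC excess (points) | LOCF excess (points), q from 0 to R |
|---|---|---|
| R = 75% | 0.8 to 8.5 | 0 to 6.75 (0.3 × 0.3 × 0.75) |
| R = 85% (assumed) | 0.9 to 9.7 | 0 to 7.65 (0.3 × 0.3 × 0.85) |

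These are differences between two ways of counting under assumed inputs. They do not estimate bias in this trial.

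**The case against.** The strongest reply is that excluding off-drug values is a coherent on-treatment choice, that Protocol 8.1.4 leaves such conventions to the SAP, and that efficacy here is secondary and descriptive. Flares seen at or before the stop are mostly kept, so the LOCF excess may be trivial. A high q sits poorly with a group that stopped for intolerable psoriasis. SAP 8.0 and SAP 11.2.2 already tabulate discontinuations by reason and adverse events leading to discontinuation, so a reader could bound the effect. All of this stands, and it limits the point to a cheap improvement. It does not supply an analysis in which failure is counted as failure, and the OC effect does not depend on q.

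Three stronger readings are tempting but unsupported.

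- *Four competing dates.* A reader might add the exposure rule, "First risankizumab dose date (either in Study M15-997 or preceding study) + 84 days", and the final-observation rule, "Final observation in the entire study is defined as the last non-missing observation collected within 140 days after the last dose of risankizumab". The first measures exposure and the second is headed as applying to safety analyses; neither is offered for efficacy. Nor would the 84-day rule settle matters. Up to Week 156 the next scheduled visit falls 70 to 98 days after the last dose (84 ± 14). If both visits are uniform and independent over their 15-day windows, about (1 + 1/15)/2 = 53% would be kept.
- *A large loss of data after Week 156.* If the home dose is not taken, the next scheduled visit is 24 × 7 = 168 days after the last dose, or 154 to 182 with windows, beyond 84 and 140 days alike. This needs a between-visit stop, late in the study, before the home dose, in a subject who stays on study. Subjects who leave have an early EOT, ideally within 2 weeks of the decision.
- *Those off-drug visits should enter LOCF and OC.* Values at 154 to 182 days lie past the 140 days that SAP 11.2.1 equates with five half-lives. They would come from subjects who stopped for any reason. If limited to values taken before new psoriasis therapy, they would often miss the worsening stoppers, who go on to rescue.

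**Conclusion.** The point holds in conditional form. SAP 10.1 removes post-discontinuation values from both methods without a date, and no planned efficacy analysis scores a stop for worsening psoriasis as non-response. The direction is certain for OC if there is any such stop and some remaining subjects respond. For LOCF it depends on whether the last value used was a response, and the excess can be near zero.

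The size is unknown. The 0.8 to 8.5 points (OC) and 0 to 6.75 points (LOCF) rest on assumed discontinuation shares, an assumed split by reason, and 75% response among subjects on drug and in other stoppers' carried values. A reader might infer that the late response rates are proven to be biased upward by several points; the documents do not support that. The primary safety objective is untouched.

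**What to change.** In SAP 10.1, add one sensitivity table for the responder endpoints, at least PASI 90 and sPGA clear or almost clear. In it, study-drug discontinuation recorded as due to worsening psoriasis or lack of efficacy, including an adverse event of worsening psoriasis that led to discontinuation, counts as non-response at all later visits. Name the eCRF reason codes and adverse event terms that identify these stops. Handling the remaining missing values as in LOCF would make the table differ from the primary one by this rule alone.

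As a clarification, state which date is meant by discontinuation of study drug in the efficacy analyses, and whether the early EOT assessment counts. Leave LOCF and OC as on-drug analyses, and do not add off-drug scheduled assessments to them.

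The cost is some SAP wording, one extra table, and slightly lower late response rates in that table. The primary reason for stopping and adverse events leading to discontinuation are already collected. The documents list no reason codes, however, so these must be checked. The SAP is to be signed before database lock, which is the time to make the change.
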